4.7 Suspension of Accrual

This study will be monitored in accordance with the Data Safety Monitoring Plan (DSMP) of the Robert H. Lurie Comprehensive Cancer Center of Northwestern University. The DSMC will review all toxicity data, and in the event of an excessive toxicity, the DSMC may require suspension of accrual.

5.0 Study Procedures

Table 4: Time and Events

Study Period	Baseline		On Treatment ¹⁰ (1 cvcle = 28 days	5)	Off Treatment Visit	Follow-Up ¹⁴
Procedures & Assessments	Screening ⁹	Day 1 of Each cycle ¹¹ (±3 days)	Day 8 and 15 of Each cycle ¹¹ (-1 to +3 days)	Response Assessments	28-Days Post Last Dose ¹³	Survival Status
Informed consent	х					
Medical history	х					
Physical exam ¹	х	х			х	х
ECOG status	Х	Х			Х	Х
Imaging ^{2, 12}	X ²			X ¹²	Х	
Hematology Labs ^{18, 9}	х	х	Х			
Chemistry Labs ^{3, 9}	Х	Х	Х			
Pregnancy test ⁴	X4		X ¹⁹			
EKG⁵	х					
Bone marrow biopsy ¹⁷	х			Х	Х	
Tissue for research ⁶	Х					
REMS® program ⁷	Х	Х				
Adverse events ⁸	Х	Х			х	
Concomitant medications	Х	Х				
Creatinine Clearance Check ²⁰		Х				
Lenalidomide treatment			X ¹⁵			
Romidepsin treatment			X ¹⁶			

¹ Physical exam should include vitals (blood pressure, heart rate, temperature, respirations), height (baseline only), and weight.

² Tumor assessment with diagnostic quality CT (chest, abdomen, pelvis; neck if clinically indicated) with or without contrast imaging within 28 days prior to registration; in addition, NM PET/CT is not required but encouraged prior to starting therapy (with or without contrast).

³ Lactate dehydrogenase (LDH), magnesium (Mg) and comprehensive metabolic panel (CMP) including albumin, alkaline phosphatase, ALT(SGPT), AST(SGOT), BUN, creatinine, electrolytes (sodium, potassium, calcium, chloride, bicarbonate), glucose, and total bilirubin.

⁴ Either urine or serum pregnancy test required within 7 days prior to registration for WOCBP; additional pregnancy testing required throughout the treatment period as outlined in the REMS® program.

⁵ EKG required within 28 days of registration (for eligibility) and then as clinically indicated thereafter.

- ⁶ If available, archived tissue from a previous biopsy is required for exploratory studies (patients who do not have available/adequate tissue may still enroll). See Section 9 for details.
- ⁷ All study participants must be registered into the mandatory REMS® program, and be willing and able to comply with the requirements.
- ⁸ SAE's will be collected from the time of consent until 30 days after treatment discontinuation.
- ⁹ All screening procedures are required within 28 days prior to registration unless otherwise indicated. Chemistry and Hematology labs are required within 14 days of registration.
- ¹⁰ Cycle 1 to begin within 14 days after registration; Treatment will continue up to 1 year unless any of the criteria in Section 4.4 are met.
- ¹¹ One cycle = 28 days ± 3 days for start of cycle. Day 8 and 15 each have a window of -1 to +3 days
- ¹² Response will be assessed with diagnostic quality CT (chest, abdomen, pelvis; neck if clinically indicated) with or without contrast imaging after cycles 3 and 6 (±7 days), and then every 6 months (±7 days). Response may be assessed more often if clinically indicated. Although not required, we encourage the use of NM PET/CT performed at baseline and repeated along the same schedule throughout (with or without contrast).
- ¹³ All patients should have a visit approximately 28 days (+/- 7 days) post-last dose of study treatment.
- ¹⁴ Once off treatment, patients will be followed clinically every 3 months (±7 days) for up to 1 year from start of study treatment, then every 6 months (±14 days) up to a total of 3 years (or until death, whichever comes first) for survival endpoints.
- ¹⁵ Lenalidomide will be given at a dose of 25 mg PO daily on days 1-21 of each cycle (followed by a 7 day break prior to the start of the next cycle). Patients will be given a medication diary to complete, which will be reviewed with a member of the study team at visits.
- ¹⁶ Romidepsin will be administered intravenously on days 1, 8, and 15 of each cycle. The dose for the first 2 cycles (6 doses total) will be 10 mg/m²; in some cases, patients may be escalated to a dose of 14 mg/m² for remaining cycles (see Section 4.1.1 for specific criteria). A window is allowed for romidepsin infusion visits (within ±3 days of day 1, and within -1 to +3 days of days 8 and 15).
- ¹⁷ Bone marrow biopsy will be done within 90 days of registration if clinically indicated, per treating physician's discretion. In patients with known bone marrow involvement at baseline, a bone marrow biopsy will be performed after the patient achieves a CR.
- ¹⁸ Complete blood count with differential will be performed weekly for the first 2 cycles, every other week for cycles 3-6, and at the start of each cycle thereafter.
- ¹⁹ Day 15 of each cycle only.
- ²⁰ Creatinine clearance will be measured and calculated prior to initiating each cycle (Refer to Appendix D for instructions on calculating creatinine clearance). The dose of lenalidomide will be adjusted per Table 1b. Any questions regarding dose calculations/adjustments should be directed to the Lead PI. Refer to Section 4.1.3 for additional information.

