3.1 Inclusion Criteria

- 3.1.1 Histologically confirmed diagnosis of PTCL (using the most recent edition of the WHO Classification of Tumors of Hematopoietic and Lymphoid Tissues as guidance) including:
 - Anaplastic large cell lymphoma, ALK-negative
 - Angioimmunoblastic T-cell lymphoma
 - Enteropathy-type T-cell lymphoma
 - Hepatosplenic γδ T-cell lymphoma
 - Peripheral T-cell lymphoma, unspecified (NOS)
 - Transformed mycosis fungoides
 - Subcutaneous panniculitis-like T-cell lymphoma

• Adult T-cell lymphoma/leukemia (ATLL) in need of systemic therapy. NOTE: Patients with adequate archived (well-preserved, formalin-fixed) biopsy tissue remaining will be required to submit a portion for exploratory studies. This is not optional if tissue is available; however, lack of adequate tissue for exploratory studies will not preclude patients from participating.

- 3.1.2 Patients must have bi-dimensionally measurable disease (≥1 cm) by CT imaging. NOTE: Patients with marrow-only disease are eligible; response for these patients will be assessed by repeat bone marrow biopsy.
- 3.1.3 Patients must fit into one of the following categories:
 - Age ≥ 18 years to < 60 years with a cumulative illness rating scale (CIRS) score ≥ 6 OR deemed ineligible for cytotoxic chemotherapy by the treating investigator (see Appendix A for CIRS scoring[42])
 - ≥ 60 years
- 3.1.4 Patients must have adequate organ and marrow function (documented within 14 days prior to registration) as outlined below:

System Laboratory Values				
Hematologic				
ANC	≥ 750/mcl			
Hemoglobin	≥ 8 g/dI			
Platelets	≥ 50,000/mcl			
Hepatic				
Total Bilirubin	≤ 2x upper limit normal (ULN)			
AST (SGOT) and ALT (SPGT)	≤ 3x ULN			
Renal				
Creatinine Clearance	≥ 30 mL/min			
See Appendix D to reference the Cockgroft-Gault equation for				
calculating creatinine clearance.				

- 3.1.5 Patients must have an ECOG performance status ≤ 2 (see Appendix B).
- 3.1.6 All patients must agree to use effective contraception while on study, and all patients must agree to undergo counseling sessions every 28 days about pregnancy precautions and risks of fetal exposure.

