4.0 Treatment Plan

Patients will be treated in cycles of 28 days (±3 days). Patients will receive romidepsin (at a dose of either 10 or 14 mg/m² – see 4.1.1 for details) IV on days 1, 8, and 15 as well as lenalidomide 25 mg PO daily on days 1- 21 of each cycle. Treatment may continue for one year or until disease progression or unacceptable toxicity. Patients who do not achieve a response of PR or better should continue to be treated only if they have SD (i.e., not PD), and if they do not have other options available that would present a more favorable risk/benefit ratio. Clinical suspicion of progressive disease (PD) or loss of response should be investigated radiographically (or by repeat bone marrow biopsy for marrow-only disease), and if confirmed, will result in removal from active therapy; such patients will remain in study follow up. In this case, it is strongly recommended that investigators consider early initiation CHOP or similar chemoimmunotherapy (off trial).

Treatment will be based on weight at baseline. Dosing should only be modified if the patient's weight has changed by more than 10% from baseline or the BSA has changed more than 5%.

It is intended that all treatments will be administered on an outpatient basis. However, treatment can be initiated during hospitalization (i.e., for newly-diagnosed patients), and can continue during unforeseen hospitalizations, but only at the discretion of the local primary investigator (PI).

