6.2.1 Complete Remission (CR)

CR requires the following:

Complete disappearance of all detectable clinical evidence of disease and disease-related symptoms if present before therapy.

1. Typically FDG-avid lymphoma: in patients with no pretreatment PET scan or when the PET scan was positive before therapy, a post-treatment residual mass of any size is permitted as long as it is PET negative.

Variably FDG-avid lymphomas/FDG avidity unknown: in patients without a pretreatment PET scan, or if a pretreatment PET scan was negative, all lymph nodes and nodal masses must have regressed on CT to normal size (\leq 1.5 cm in their greatest transverse diameter for nodes > 1.5 cm before therapy). Previously involved nodes that were 1.1 to 1.5 cm in their long axis and more than 1.0 cm in their short axis before treatment must have decreased to \leq 1.0cm in their short axis after treatment.

- 2. The spleen and/or liver, if considered enlarged before therapy on the basis of a physical examination or CT scan, should not be palpable on physical examination and should be considered normal size by imaging studies, and nodules related to lymphoma should disappear. However, determination of splenic involvement is not always reliable because a spleen considered normal in size may still contain lymphoma, whereas an enlarged spleen may reflect variations in anatomy, blood volume, the use of hematopoietic growth factors, or causes other than lymphoma.
- 3. If the bone marrow was involved by lymphoma before treatment, the infiltrate must have cleared on repeat bone marrow biopsy. The biopsy sample on which this determination is made must be adequate (with a goal of > 20 mm unilateral core). If the sample is indeterminate by morphology, it should be negative by immunohistochemistry. A sample that is negative by immunohistochemistry but that demonstrates a small population of clonal lymphocytes by flow cytometry will be considered a CR until data become available demonstrating a clear difference in patient outcome.

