6.2.2 Partial Response (PR)

PR requires the following:

- At least a 50% decrease in sum of the product of the diameters (SPD) of up to six of the largest dominant nodes or nodal masses. These nodes or masses should be selected according to all of the following: they should be clearly measurable in at least 2 perpendicular dimensions; if possible they should be from disparate regions of the body; and they should include mediastinal and retroperitoneal areas of disease whenever these sites are involved.
- 2. No increase should be observed in the size of other nodes, liver, or spleen.

- 3. Splenic and hepatic nodules must regress by ≥ 50% in their SPD or, for single nodules, in the greatest transverse diameter.
- 4. With the exception of splenic and hepatic nodules, involvement of other organs is usually assessable and no measurable disease should be present.
- 5. Bone marrow assessment is irrelevant for determination of a PR if the sample was positive before treatment. However, if positive, the cell type should be specified (e.g., large-cell lymphoma or small neoplastic B-cells). Patients who achieve a CR by the above criteria, but who have persistent morphologic bone marrow involvement will be considered partial responders. When the bone marrow was involved before therapy and a clinical CR was achieved, but with no bone marrow assessment after treatment, patients should be considered partial responders.
- 6. No new sites of disease should be observed.
- 7. Typically FDG-avid lymphoma: for patients with no pretreatment PET scan or if the PET scan was positive before therapy, the post-treatment PET should be positive in at least one previously involved site.

Variably FDG-avid lymphomas/FDG-avidity unknown: for patients without a pretreatment PET scan, or if a pretreatment PET scan was negative, CT criteria should be used.

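### The protocol gives conflicting rules for assessing response in marrow-only patients, and its PR wording can count one as a responder with no marrow improvement.

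*Combined protocol and SAP*

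**What the plan says.** The provisions that bear on a patient whose only disease site is the marrow are spread over several sections.

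- **Section 3.1.2** requires disease measurable by CT but exempts marrow-only patients, for whom "response for these patients will be assessed by repeat bone marrow biopsy". It gives no time point.
- **Table 4** marks bone marrow biopsy at Screening, Response Assessments and the Off Treatment Visit. The whole row refers to footnote 17.
- **Footnote 17** gives one post-baseline instruction, for anyone whose marrow was known to be involved at the start: "a bone marrow biopsy will be performed after the patient achieves a CR".
- **Footnote 12** defines the scheduled response assessments (after cycles 3 and 6, then every 6 months) by CT and does not mention biopsy.
- **Section 6.2.1 item 3**, on CR: "If the bone marrow was involved by lymphoma before treatment, the infiltrate must have cleared on repeat bone marrow biopsy".
- **Section 6.2.2 item 1** defines PR by at least a halving of the summed products of nodal diameters.
- **Section 6.2.2 item 5** makes the marrow irrelevant to PR if it was positive at baseline, and then assigns PR in two situations. One is CR on the other criteria with a marrow that is still morphologically positive. The other is "When the bone marrow was involved before therapy and a clinical CR was achieved, but with no bone marrow assessment after treatment".
- **Section 4.0** has suspected progression or loss of response checked "by repeat bone marrow biopsy for marrow-only disease".
- **Section 7.4** stops the study if 6 or fewer of the first 12 patients have CR or PR at the 3-month assessment. Section 10.1 sets the final ORR on 20 evaluable patients.

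**The concern.** The adopted response criteria are written for patients with nodal or other measurable disease, in whom the marrow is a secondary check. Section 3.1.2 makes an exception to measurable disease, but no CR, PR or SD rule follows for the patients it admits. Two problems result.

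The first is timing. Read literally, footnote 17 waits for a CR that item 3 of 6.2.1 will not grant until the biopsy has been done. Nothing in the text clearly places a marrow result at the cycle 3 assessment, which feeds the interim count.

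The second is classification. The two PR sentences in 6.2.2 item 5 are sensible when shrinking nodes already show a response and the marrow only separates CR from PR. When the marrow is the sole site, the same sentences can turn a still-positive or untested marrow into a PR.

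Two sites following the protocol could therefore classify identical patients differently on the primary endpoint, in a study of 20.

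**Working it through.** **1. The rules applied to a marrow-only patient at cycle 3**

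| Situation | Rule that applies | Result |
|---|---|---|
| Biopsy done, marrow cleared, rest of CR met | 6.2.1 item 3 | CR |
| Biopsy done, marrow still positive, rest of CR met | 6.2.2 item 5, persistent involvement | PR |
| No biopsy, clinical CR accepted | 6.2.2 item 5, no later marrow | PR |
| No biopsy, clinical CR not accepted | CR not available; PR item 1 has no nodes to measure | Not a responder |

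The second and third rows give a responder without evidence that the marrow improved. The fourth gives a non-responder without evidence that it did not. Only the first rests on a favourable marrow finding.

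**2. The plan's own precision figure**

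Section 10.1: 1.96 × 0.5/√20 = 0.219, which agrees with the stated 0.22. The precision figure is not in dispute. It gives a scale for what follows.

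**3. Effect on the final ORR**

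One classification out of 20 is 1/20 = 5 percentage points, against a half width of about 22 points.

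**4. Effect on the interim rule**

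Inputs: 12 patients, stop at 6 or fewer responders (Section 7.4). The documents give no number of marrow-only patients, so m = 0, 1 or 2 among the first 12 is an assumption. The true ORR of 50% is also an assumption. Section 10.1 reports that rate for the combination in relapsed or refractory disease, and says that the front-line setting is untested.

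If m patients are counted as PR regardless of marrow, the other 12 − m must supply no more than 6 − m responders for a stop:

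- m = 0: P(X ≤ 6 | 12, 0.5) = 2510/4096 = 0.613
- m = 1: P(X ≤ 5 | 11, 0.5) = 1024/2048 = 0.500
- m = 2: P(X ≤ 4 | 10, 0.5) = 386/1024 = 0.377

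If one such patient is counted as a non-responder regardless of marrow:

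- P(X ≤ 6 | 11, 0.5) = 1486/2048 = 0.726

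**5. Other true rates (probability of a futility stop)**

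| True ORR | m = 0 | 1 counted as PR | 2 counted as PR | 1 counted as non-responder |
|---|---|---|---|---|
| 40% | 0.842 | 0.754 | 0.633 | 0.901 |
| 50% | 0.613 | 0.500 | 0.377 | 0.726 |
| 60% | 0.335 | 0.247 | 0.166 | 0.467 |

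Across this range, one patient counted as PR by rule lowers the stopping probability by 9 to 11 points. One counted as a non-responder raises it by 6 to 13 points.

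**The case against.** The best defence is that Section 3.1.2 is the specific provision for this group and attaches no CR condition to the repeat biopsy. Table 4 marks biopsy at response assessments and off treatment, Section 4.0 calls for it when progression is suspected, and footnote 17 does not contain the word only. If CR in footnote 17 means the clinical CR of 6.2.2 item 5, the circularity disappears and the footnote describes an ordinary confirmatory biopsy.

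Much of this stands. A reader might infer that marrow-only patients are denied a biopsy until CR, or that they become responders automatically. The documents support neither inference. They conflict on timing; they do not consistently withhold the biopsy. The sentence ending "but with no bone marrow assessment after treatment, patients should be considered partial responders" needs both a clinical CR and no post-treatment marrow. Clinical CR under 6.2.1 asks for more than a clear CT: symptoms of the disease must have resolved, and an enlarged liver or spleen must be normal again. If the biopsy in 3.1.2 is done, this default does not arise.

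The defence does not remove the problem. Footnote 17 does not say clinical CR. Section 4.0 covers only suspected progression or loss of response. Reading footnote 17 as clinical CR leads to the neighbouring sentence in item 5, under which a biopsy that is done and still positive yields a PR. In a patient with no nodal disease and few symptoms, the clinical CR that this sentence builds on may need little or no change.

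It is also fair to say that the number of marrow-only patients is unknown, and that tying response to marrow clearance is an endpoint rule going beyond the adopted criteria.

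**Conclusion.** The concern holds as an internal contradiction with a consequence for the primary endpoint. Sections 3.1.2, Table 4 with footnotes 12 and 17, and 6.2.1/6.2.2 do not together say when a marrow-only patient's response biopsy is done or how its result is classified. Following 6.2.2 item 5 as written can count such a patient as a responder with no marrow improvement.

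The size is conditional. It is zero if no marrow-only patient enrols. With one or two among the first 12 and a true ORR of 50%, the chance of a futility stop moves from 61% to 50% or 38% in one direction, or to 73% for one patient in the other. Both the count and the rate are assumptions. The 5-point shift in the final ORR per classification depends only on the 20 evaluable patients. The point should be corrected, but it does not undermine the design.

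**What to change.** 1. Reconcile Section 3.1.2, Table 4 with footnote 17, and Sections 6.2.1 and 6.2.2. State which response assessment the biopsy in 3.1.2 supports, and whether it informs the 3-month interim count. This should not add biopsies beyond those that 3.1.2 and Table 4 already provide for.
2. State that, for the ORR and the interim count, the two PR sentences of 6.2.2 item 5 do not apply when the marrow is the only disease site. Such patients count as responders only on documented marrow clearance, and as non-responders if there is no post-treatment marrow.
3. Report the number of marrow-only patients among the first 12 and among the 20 evaluable, so that a reader can see how far the rule matters.

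The cost is wording in one footnote and the endpoint section. The second change removes PR as a category for this small group, which departs from the adopted criteria and should be stated openly. The ORR may be slightly less favourable as a result.

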6.0 Assessment of Endpoints

6.1 Toxicity Endpoints

The frequency and severity of adverse events will be assessed once per cycle according the NCI-CTCAE version 4.03. All patients who receive at least one dose of either study drug will be evaluable for toxicity endpoints.

6.2 Efficacy Endpoints

Response and progression will be evaluated using the 2007 Revised Response Criteria for Malignant Lymphoma (RRCML) as defined by Cheson, et al.[43] See Table 5 for a summary of the follow definitions:

6.2.1 Complete Remission (CR)

CR requires the following:

Complete disappearance of all detectable clinical evidence of disease and disease-related symptoms if present before therapy.

1. Typically FDG-avid lymphoma: in patients with no pretreatment PET scan or when the PET scan was positive before therapy, a post-treatment residual mass of any size is permitted as long as it is PET negative.

Variably FDG-avid lymphomas/FDG avidity unknown: in patients without a pretreatment PET scan, or if a pretreatment PET scan was negative, all lymph nodes and nodal masses must have regressed on CT to normal size (\leq 1.5 cm in their greatest transverse diameter for nodes > 1.5 cm before therapy). Previously involved nodes that were 1.1 to 1.5 cm in their long axis and more than 1.0 cm in their short axis before treatment must have decreased to \leq 1.0cm in their short axis after treatment.

- 2. The spleen and/or liver, if considered enlarged before therapy on the basis of a physical examination or CT scan, should not be palpable on physical examination and should be considered normal size by imaging studies, and nodules related to lymphoma should disappear. However, determination of splenic involvement is not always reliable because a spleen considered normal in size may still contain lymphoma, whereas an enlarged spleen may reflect variations in anatomy, blood volume, the use of hematopoietic growth factors, or causes other than lymphoma.
- 3. If the bone marrow was involved by lymphoma before treatment, the infiltrate must have cleared on repeat bone marrow biopsy. The biopsy sample on which this determination is made must be adequate (with a goal of > 20 mm unilateral core). If the sample is indeterminate by morphology, it should be negative by immunohistochemistry. A sample that is negative by immunohistochemistry but that demonstrates a small population of clonal lymphocytes by flow cytometry will be considered a CR until data become available demonstrating a clear difference in patient outcome.

